6.8 AUTHORIZED ASSOCIATED TREATMENT

All the treatments judged necessary are allowed and left to the discretion of the investigator.

6.9 PROHIBITED ASSOCIATED TREATMENTS

No treatments are prohibited in this study.

7. DATA COLLECTION

All data described above will be recorded in the study Electronic Case Report Form (e-CRF) (see Section 8.2).

8. STUDY MONITORING AND DATA MANAGEMENT

8.1 STUDY MONITORING

Representatives of STAGO must be allowed to visit or remotely monitor all study site locations periodically to assess the data quality and study integrity. The sites will be monitored by Stago clinical personnel or by qualified clinical staff from a Contract Research Organisation (CRO) that will be selected by Stago. Monitors' qualification, extent of Source Data Verification (SDV), timing and frequency of monitoring visits, possibility to perform remote monitoring, the essential documents to be reviewed and other study specific monitoring requirements will be addressed in a separate document that will be developed by STAGO and the CRO. Monitoring will include periodic review of the data to ensure that the investigators are in compliance with the protocol, the clinical trial agreement and the applicable regulations. Study records will be reviewed and compared against source documents and any discrepancies will be resolved.

Representatives of STAGO and/or the CRO will meet with the investigator prior to the initiation of the study in order to review the adequacy of the patient population, facilities, and equipment with respect to the needs of the study, and to familiarize the investigator with the study protocol.

At study initiation study monitors will visit the site in order to ensure that patients are being properly selected, that the methods described in the study protocol are understood and that data are being correctly recorded.

During the course of the study the monitors will either conduct on-site or remote review of the source documents and compare with the reported data into the electronic Case Report Forms (eCRF). Upon completion of the study the monitors will notify the site of closeout and a study closeout visit will be performed either on-site or remotely.

8.2 DATA ENTRY

All sites participating in this study will use e-CRF for all data.

The integrated procedures in production, development, test and maintenance will be thoroughly audited and fully documented in compliance with 21 CFR Part 11.

Checks for occurrence, probability, and coherence will be made simultaneously with, or as quickly as possible after, data entry. The investigator is warned of any errors detected and can take action immediately. In addition, monitors and data manager(s) can follow the quality of the data input in real time and perform check of forms on line. Each modification is made by clicking on the item, which generates a change that the investigator validates electronically.

- Certification of the data

The data signature can follow immediately after the data input, or after an email request for validation is sent to the center investigator. A formatted version of the data can be submitted to the center investigator for control and validation at any time.

- Security

Each individual with access to the eCRF will have a user name and a password associated with a profile that defines user access level (access denied, read-only access, read-write capability) on each function of the application. For example, center investigators have full access to their patient data, not those of the other centers but they can consult them.

8.3 DATA MANAGEMENT

The data management will be delegated to a CRO. The CRO will also be responsible for the development of the primary database for the study as well as the quality control of the database and confirming the overall integrity of the data.

Corrections are made through the electronic data capture tool, which generates an automated audit trail including date and timestamp, full name of the person making the correction and the original entry. The system also prompts the user to document the reason for change which is also retained in the audit trail.

9. STATISTICAL CONSIDERATIONS

9.1 OVERVIEW

The primary aim of this study is to demonstrate the ability of the STA® - Liatest® D-Di XL (Device) to exclude VTE in subjects with low or moderate pre-test probability (PTP) for each indication separately (PE and DVT), as quantified by NPV; subjects with low or moderate pre-test probability are collectively labeled “unlikely.” Additionally, this study aims to demonstrate the sensitivity of STA® - Liatest® D-Di XL in the “unlikely” population of the indications noted. Primary statistical testing and success criteria for this trial are taken from FDA approved CLSI guidelines.

Enrolment in the DVT and PE groups will be monitored separately. Ideally, recruitment rates will be similar in the two groups in which case analyses for both will be done at about the same time and a single regulatory submission will include both indications. If this is not the case, statistical analyses will be done separately and, if needed, submissions will be done separately as well. The statistical analysis plans (SAPs) for PE and DVT will be finalized and signed prior to data lock for the first indication completed, (should the indications differ in data lock times). This will enable using data from patients with both indications—i.e. patients suspected of having both PE and DVT—to be included in the analyses of the separate indications

9.2 DESIGN CONSIDERATIONS

This is a prospective, multi-center study which will recruit consecutive subjects suspected of VTE. The population of interest includes those subjects classified “unlikely” by the Wells score system as specified in the CLSI guideline.

Following are central elements of this trial's design:

Separate Statistical Testing of DVT and PE: Logistically this trial will be conducted as a single study. However data obtained will be analyzed separately for DVT and PE subjects. Trial design is identical for both indications and statistical analyses are almost identical.

Blinding of follow-up data: All "unlikely" subjects excluded at Visit 1 by SOC D-dimer negative or by negative imaging will be followed for occurrence of VTE for up to three months. To minimize possible bias during follow-up:

- Testing of STA® - Liatest® D-Di XL will be performed by testing site staff blinded to imaging or follow up results. A procedure will be set up before testing starts to ensure that blinding is rigorously maintained at testing sites
- Stago will be exposed to recruitment rates and count of reference-positive cases for the purpose of blind sample size re-estimation. Company will be blinded to all other data (including, of course, device outcome). A standard operating procedure (SOP) will be developed to ensure that this in fact is the case.
- Company and designated statisticians will be blind to efficacy data throughout the trial. The electronic data capture (EDC) provider will create a file accessible to data management and statistics that includes all study data excluding Device result (level of D-dimer) and Device diagnosis (positive or negative). This will enable counting reference-positive cases blind to outcome, which is needed for blind sample size re-estimation. The provider will create a separate file that is accessible to the provider only, in which subjects' D-dimer results are entered. Files will be merged at data lock, after the final SAPs have been completed and signed. The procedure will be drawn up in an SOP.

STA® - Liatest® D-Di XL testing for the purpose of this trial will be done on banked samples collected from subjects at Visit 1.

Special efforts will be made by PI (or his/her team) to obtain follow-up clinical outcome for subjects who could not initially be reached by the standard follow-up procedures. Such efforts may include attempts to trace subjects through relatives and examination of State death records.

Ensuring Requisite Power: The co-primary hypotheses in this trial relate to NPV and Sensitivity. To obtain requisite power for both co-primary endpoints a minimal number of VTE positive cases (for testing sensitivity) and D-Di negative cases (for testing NPV) is needed. Our computations indicate that having a sufficient number of VTE positive cases for testing sensitivity will, due to low VTE positive prevalence, yield a sufficient number of D-Di negative cases as well; when power for sensitivity is near the desired 90%, power for NPV is near 100%. Thus, determination of sample size is driven by the trial's requirement for sensitivity.

The trial will conclude after enough VTE positive cases have been recruited to achieve requisite power.

As noted in Section 4.2 blood samples will be tested for stability using the VIDAS D-dimer assay and only those determined stable will be included in this study (and tested with STA® - Liatest® D-Di XL). It is important to note that:

- a. VIDAS® D-Dimer Exclusion II assay was chosen because its precision is highest of all FDA approved assays in the indication. Greater precision is expected to yield a better assessment of stability since measurement error (random variation in outcome) may cause sample to be wrongly classified as “unstable”.
- b. A blood sample that has been frozen and thawed, and shown stable by testing (within acceptable error) is equivalent to the fresh sample. Consequently, testing stable frozen/thawed samples with STA® - Liatest® D-Di XL is equivalent to having tested the sample fresh.

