9.4 ANALYSIS SETS

The Primary efficacy analysis set will consist of all "unlikely" VTE subjects for whom there are valid observed values on both STA® - Liatest D-Di XL and Reference Standard (imaging or follow up). This includes "unlikely" subjects suspected of PE, or DVT or both; the latter will be included in both of the separate PE and DVT analysis sets. "Unlikely" D-dimer negative subjects having imaging result at Visit 1 will have imaging as reference. Device result is considered valid if it is not missing, its associated QC results are in the QC ranges and is deemed stable after thawing according to criteria provided in Section 4.2. Subjects with major protocol deviations likely to affect outcome will be excluded by blind review³. In line with CLSI guidelines, distal DVT subjects are not included in the primary efficacy analysis set for the DVT indication.

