⁵ Achieving requisite power for sensitivity, rather than NPV, drives the sample size

At the time this protocol amendment is issued, a total of 3,054 PE patients were enrolled including 121 PE positive patients (79 in US and 42 OUS - uncleaned, non-final data), allowing to have 90% power to demonstrate D-Di XL efficacy for PE. The PE data collection has been completed and data cleaning is in progress.

DVT: Power for Meeting PGs

Presentation of sample size is based on obtaining enough reference-positive case to achieve 90% power to meet the confidence interval PG for sensitivity (≥ 0.90), which will necessarily provide:

- The same power to meet the point estimate PG, since the minimum true-positives needed to meet the confidence interval PG is the same as that needed to meet the point estimate PG.
- A sufficient number of reference-negative patients for near 100% power to meet the PGs for NPV, due to low prevalence of positive cases

Based on data previously submitted to FDA, we assume:

- US prevalence of reference-positive = 5.3%
- OUS prevalence of reference-positive = 8.1%
- D-Di XL sensitivity = 98%
- D-Di XL NPV = 99.6%

Given the above, $N = 115$ reference-positive subjects are needed to have 90% power to demonstrate efficacy. Given at least $N = 69$ in the US (60%), at least 1,032 “unlikely” US subjects will be needed ($69/0.053$). Given $N = 46$ OUS (40%) 568 “unlikely” OUS subjects will be needed ($46/0.081$).

In summary, a total of 1,870 subjects are expected to participate in the DVT part of the study—at least 1,032 from the US and at most 568 from OUS—to have 90% power to demonstrate D-Di XL efficacy for DVT.

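### If PE locks before DVT, a blind DVT exclusion review cannot be assured for subjects suspected of both conditions

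*Combined protocol and SAP*

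**What the plan says.** On blinding, section 9.2 states: "Company and designated statisticians will be blind to efficacy data throughout the trial". Device results sit in a separate file that only the data capture provider can open. The same bullet sets the moment of joining: "Files will be merged at data lock, after the final SAPs have been completed and signed". Two SOPs are promised, one on what the company may see and one on the file procedure.

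On timing, section 9.1 hopes for similar recruitment in the two groups. Failing that, "statistical analyses will be done separately and, if needed, submissions will be done separately as well". The safeguard for different lock times is that the PE and DVT SAPs "will be finalized and signed prior to data lock for the first indication completed", with the stated purpose: "This will enable using data from patients with both indications".

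On the overlap, section 9.4 says of subjects suspected of both conditions that "the latter will be included in both of the separate PE and DVT analysis sets".

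On exclusions, section 9.4 states: "Subjects with major protocol deviations likely to affect outcome will be excluded by blind review". Section 11 gives that review to the sponsor with CRO support and removes subjects with major deviations from the study.

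On status at amendment 2.1, section 9.5 reports: "The PE data collection has been completed and data cleaning is in progress". The synopsis says DVT enrolment is still open.

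**The concern.** A dual-suspected subject has a banked plasma sample whose device result serves both analyses. Under section 9.2, data management and statistics already work with a file holding everything except the device result and device diagnosis. For them the device result is the only hidden item, and a PE merge would uncover it. If DVT is still open at that point, any later decision on whether such a subject has a major DVT deviation could be taken by people who know that the subject is a false negative.

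The decision is a judgement about whether a deviation is likely to affect outcome, and the sponsor makes it. The DVT sensitivity goal turns on very few subjects, so a single exclusion can decide it. Once results have been seen, blinding cannot be restored.

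**Working it through.** **Chain of provisions**

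1. Device results join the other data at lock (9.2).
2. The two locks may fall at different times (9.1).
3. Dual-suspected subjects are in both sets (synopsis, 9.4), so a PE merge includes them.
4. DVT exclusions for major deviations rest on a blind review run by the sponsor (9.4, 11).
5. Nothing in the protocol completes and freezes the DVT decisions on these subjects before a PE merge, or assigns the DVT review to people without access to PE results.

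Steps 1 to 4 are stated. That the DVT review would follow a PE lock is an inference from DVT still enrolling.

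**Inputs for the size.** From 9.5 and 9.6: 115 reference-positives, assumed sensitivity 0.98, exact two-sided 95% lower limit (LCL) at least 0.90, point estimate at least 0.95.

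**The plan's own figure.** The exact lower limit for x true positives out of n is the 0.025 quantile of Beta(x, n − x + 1).

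- 110/115: LCL 0.9015, estimate 0.957. Passes.
- 109/115: LCL 0.8899, estimate 0.948. Fails both goals.

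Success therefore needs at most 5 false negatives (FN). With FN ~ Binomial(115, 0.02), P(FN ≤ 5) = 97.1%, so the plan's claim of at least 90% power holds. At true sensitivity 0.90 the chance of passing is 2.2%.

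**One exclusion.** Removing one false negative from 109/115 gives 109/114: LCL 0.9006, estimate 0.956. Passes both goals.

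**Upper bound.** If one false negative could always be removed, the success criterion changes from FN ≤ 5 to FN ≤ 6 out of 115:

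| True sensitivity | P(FN ≤ 5) | P(FN ≤ 6) |
|---|---|---|
| 0.90 | 2.2% | 5.1% |
| 0.95 | 48% | 65% |
| 0.98 | 97.1% | 99.1% |

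**Allowing for the overlap.** Its size is not given, so assume that 6, 12 or 23 of the 115 positives (about 5%, 10% or 20%) are dual-suspected. The chance that at least one of m dual positives is a false negative is 1 − sensitivity^m:

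| m | at 0.98 | at 0.95 |
|---|---|---|
| 6 | 11% | 26% |
| 12 | 22% | 46% |
| 23 | 37% | 69% |

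One removal changes the outcome only when there are exactly 6 false negatives and at least one of them is dual. If the 6 fall at random among the 115, the chance that at least one is dual is 1 − C(115 − m, 6)/C(115, 6) = 28%, 49% or 75% for m = 6, 12, 23. Multiplying by P(FN = 6), which is 2.9%, 16.4% and 2.0% at sensitivity 0.90, 0.95 and 0.98:

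| m | at 0.90 | at 0.95 | at 0.98 |
|---|---|---|---|
| 6 | 0.8% | 4.6% | 0.6% |
| 12 | 1.4% | 8.1% | 1.0% |
| 23 | 2.2% | 12.2% | 1.5% |

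These are still ceilings, because the subject must also have an undecided DVT deviation that could be called major.

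**The case against.** The case against is substantial, and much of it stands.

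- **No PE-first lock is scheduled.** Lock needs device testing as well as enrolment, and testing waits for the assay to be ready. Both indications could still lock together, and then the issue does not arise. A reader might infer from the PE status report that an early PE lock was decided. The documents show only that it is allowed and plausible.
- **The plan did foresee dual-suspected subjects.** Signing both SAPs before the first lock protects the analysis methods. It does not settle which individuals are excluded.
- **Section 11 may carry decisions over.** Exclusion there is from the study, so a blind decision made for PE might also bind DVT. Nothing says that such decisions are final for DVT or cover deviations specific to the DVT work-up.
- **Sample validity leaves little discretion.** Stability limits and QC ranges are fixed criteria. The exposure is confined to judgement-based deviations still open at a PE lock.
- **An exclusion made with knowledge of the result would breach the plan.** Sections 9.4 and 11 require blind review. That is true, but the protocol does not say how blindness would be kept for the overlap.
- **The promised SOPs may govern access after the merge.** They are not among the documents, and the protocol does not say who at the sponsor would see subject-level PE results. It is therefore too strong to say that the sponsor will see them. They could be seen.
- **The blinding sentence can be read as running to each lock.** This is a fair reading, but under staggered locks the literal wording does not hold for the overlap and should say what is meant.

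**Conclusion.** The point holds conditionally. If PE is locked and analysed first, the protocol as written cannot assure either the blinding promised in 9.2 or the blind exclusion review in 9.4 and section 11 for dual-suspected subjects. DVT-only subjects are unaffected.

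A reader might conclude that the DVT false-positive rate becomes 5.1%. The documents do not support that. The figure assumes that a removable false negative is always available among dual-suspected subjects and is always excluded. At the planned sensitivity the same assumption adds only 2 percentage points (97.1% to 99.1%). Nor is there any evidence of intended or actual selective exclusion. This is a route to bias left open, not a bias shown.

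Severity is low to moderate. It rests on a staggered lock, on DVT deviation decisions still open at the first merge, and on an overlap whose size is not stated.

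**What to change.** In sections 9.1 and 9.2, and in both SAPs, state that if the indications lock at different times:

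1. the blind deviation and reference-status review of all dual-suspected subjects is completed, signed and frozen for both indications before any device results are merged;
2. the first merge covers only subjects in the analysis set of the indication being locked;
3. blinding of the company and statisticians holds until lock of the respective indication, replacing the present wording.

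The cost is one earlier blind-review session for the dual-suspected subset and a few sentences of text. Follow-up under section 6.7 already asks about both DVT and PE, so the session should need little or no extra data. The text must be in force before the first merge. If both indications lock together, it costs almost nothing.

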9.3 ENDPOINTS

Primary Efficacy

For each "unlikely" subject, VTE diagnosed dichotomously (positive/negative) by:

- Reference Standard, which includes data obtained by imaging or follow-up,
- Device

9.4 ANALYSIS SETS

The Primary efficacy analysis set will consist of all "unlikely" VTE subjects for whom there are valid observed values on both STA® - Liatest D-Di XL and Reference Standard (imaging or follow up). This includes "unlikely" subjects suspected of PE, or DVT or both; the latter will be included in both of the separate PE and DVT analysis sets. "Unlikely" D-dimer negative subjects having imaging result at Visit 1 will have imaging as reference. Device result is considered valid if it is not missing, its associated QC results are in the QC ranges and is deemed stable after thawing according to criteria provided in Section 4.2. Subjects with major protocol deviations likely to affect outcome will be excluded by blind review³. In line with CLSI guidelines, distal DVT subjects are not included in the primary efficacy analysis set for the DVT indication.

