- 1) The initial phase (see diagram below) will include sample and data collection from subjects suspected of VTE (PE and/or DVT) at participating sites (“enrolling sites”); subjects will be diagnosed and treated in accordance with routine standard of care (SOC). A test using VIDAS® D-Dimer Exclusion II™ (VIDAS) assay will be conducted on one of the frozen plasma aliquots. The result obtained (i.e. D-Di “reference value”) will be used in the following phase to assess sample stability.

- 2) When the STA® - Liatest® D-Di XL product is ready for clinical testing (see diagram below), frozen samples from unlikely patients will be tested with VIDAS assay and with STA® - Liatest® D-Di XL. The results of the VIDAS assay will be used to assess samples stability. The results from “stable” samples will be used for comparison to reference (imaging or follow-up) and computation of accuracy parameters (sensitivity, NPV, specificity and PPV). STA® - Liatest® D-Di XL and stability testing will be performed at selected sites (“testing sites”). There will be at least 2 testing sites in the US and 2 in Europe.

Procedures for STA - Liatest DDi XL clinical testing

Main inclusion criteria: The study population will be recruited from prospective, consecutive, ambulatory outpatients (presenting at the emergency unit or outpatient clinic) suspected of having VTE. Patients with DVT and PE will be analyzed as separate groups. Therefore, enrolment in each group will be monitored separately and will be stopped when the desired target per indication is reached. Subjects suspected of both DVT and PE will be included in both PE and DVT groups.

Number of Subjects

A sample size of $N = 115$ evaluable reference-positive subjects is needed to achieve at least 90% power to demonstrate sensitivity for PE and DVT separately. This will provide at least 80% power to demonstrate co-primary performance goals for PE and co-primary performance goals for DVT. The samples needed to obtain the number of positives will, due to low prevalence, yield a large number of negative subjects so that power for demonstrating NPV performance goals is about 100% in each indication.

Expected overall study enrolment – PE

Based on actual prevalence data obtained during enrolment, a total of at least 2,908 subjects were expected to participate in the PE study—with at least 2,206 from the US and at least 702 from OUS—to have 90% power to demonstrate STA® - Liatest® DDi XL efficacy for PE.

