6. STUDY PROCEDURES

6.1 SCREENING

Prospective, consecutive ambulatory outpatients (presenting to the emergency unit or outpatient clinic) suspected of having VTE will receive an explanation about the study, will be screened for eligibility using the inclusion and exclusion criteria (see Section 5.1). If the patient is eligible, he/she will be

Country-specific amendment for US sites

offered the possibility to participate in the study and go through the informed consent process (see Section 14.1) These patients will then be evaluated using the Wells score and procedures according to SOC for VTE diagnosis at the site.

As patients eligible in this study require emergency procedures/tests to be performed, it is possible that D-Dimer test or VTE diagnosis are completed before the investigator has the possibility to obtain patient written consent to participate in the study. Therefore, **this procedure will not be considered a protocol deviation** as long as the Investigator is blinded to the result of the D-Dimer test or to final VTE diagnosis at the time of patient screening.

The relevant demographic characteristics, medical history and concomitant medication treatment of the enrolled patients will be reported.

Three months follow-up information may be recorded directly in the CRF, in this case the CRF will be considered as Source Document.

A register may be kept for:

- all screening failure patients, including reasons for non-inclusion
- patients screened and satisfying the criteria for inclusion/exclusion but for whom a final VTE diagnosis according to site's SOC is not available will be excluded from the study. These patients will be reported, as well as the reasons for their missing diagnosis.

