6.2 VTE DIAGNOSIS AND STUDY PROCEDURES

At all sites, VTE diagnosis will follow SOC procedures for diagnosis and treatment.

For patients suspected of VTE, this may include imaging only, or D-Dimer test followed by imaging or PTP score + D-Dimer testing + imaging. For all patients for whom VTE is not confirmed by imaging at the initial visit, the study will require that a 3-month follow-up is performed.

- Irrespective of the procedures used locally for VTE diagnosis, sites will be asked to evaluate patients with symptoms consistent with VTE (DVT and/or PE) using the Wells score without knowledge of D-Dimer and/or imaging results. The Wells score result may or may not be used for VTE diagnosis depending on sites' SOC.
- About 12 ml of venous blood will be taken from unlikely subjects (see definition on page 10) in order to obtain at least 6 aliquots of 1 mL of patient plasma each: plasma aliquots will then be banked frozen at -70°C
- STA® - Liatest® D-Di XL will later be used on banked frozen samples to assess assay's accuracy relative to the reference standard (imaging or 3-month follow-up). Only samples determined stable using the procedure described in Section 4.2 will be included in the study.
- Samples may also be used in future studies to evaluate new D-dimer test products to be used as improved diagnostic tools for DVT and/or PE (currently under development by Stago).

Plasma from patients with high Wells score will not be collected in the study.

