6.7 FOLLOW UP

Patients for whom VTE was excluded as per SOC will be followed for 3 months to evaluate potential development of DVT and/or PE.

This follow-up will be performed by the clinician, the study coordinator or the nurse to obtain information regarding development of DVT and/or PE in the 3 months (i.e. 90 days) following Visit 1. The follow-up will have an allowed window of 1 month. Therefore it will take place in the period between 3 and 4 months (i.e. 90 to 120 days) after patient's first visit. The follow-up may be done using several methods according to site choice:

- Phone call to the patient,
- Medical record review if at enrollment patient states he/she does all its medical consultation at the investigation site and if he/she agrees that follow-up will be done by review of its medical record,
- Email to the patient asking the patient to call one site study representative if patient has given its consent to be contacted via email and server for email is secure,
- Call to family doctor in case patient is not answering the call.

The three-months follow-up information may be recorded directly in the CRF, in this case the CRF is considered as Source Document.

In addition, for female patients pregnant at the time of the follow up contact, all efforts will be done to determine if patient had an undetected pregnancy at visit 1, in which case the patient will be excluded from the study due to violation of an exclusion criterion.

If a patient cannot be contacted to collect follow-up information even beyond the 120 days from visit 1, he/she will be considered "lost to follow-up". But before declaring that a patient is "lost to follow-up", the PI (or his/her team) must do his/her best effort to contact patients and attempts should be made via all available routes, and when necessary, patients should be traced through relatives and examination of State death records. A certified letter should be sent to the permanent address on file. The methods used to attempt to contact the patient should be noted.

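### Does a subject suspected of both PE and DVT, confirmed for one and never worked up for the other, leave the second analysis set without a usable reference?

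*Combined protocol and SAP*

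**What the plan says.** The synopsis states that "Subjects suspected of both DVT and PE will be included in both PE and DVT groups", and section 9.4 repeats the idea for the analysis sets: "the latter will be included in both of the separate PE and DVT analysis sets". The sentence in 9.4 just before it restricts the primary efficacy set to subjects with valid observed values on both the device and the reference standard, the latter by imaging or follow-up.

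Under section 6.2, "VTE diagnosis will follow SOC procedures for diagnosis and treatment", so the study does not require imaging of both sites in a dual-suspect. Follow-up is tied to VTE as one entity. Section 6.2 requires it for patients "for whom VTE is not confirmed by imaging at the initial visit, the study will require that a 3-month follow-up", and 6.7 says "Patients for whom VTE was excluded as per SOC will be followed for 3 months". What it collects is wide: 6.7 asks sites "to obtain information regarding development of DVT and/or PE in the 3 months", and under 9.2 subjects "will be followed for occurrence of VTE for up to three months".

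Sections 3.1 and 9.3 word the endpoint as VTE positive or negative. Section 9.5 works by indication, with separate prevalences and a count of 121 PE positives among 3,054 PE patients. Section 9.1 announces SAPs for PE and for DVT, both to be signed before the first data lock so that dual-suspects can serve both analyses. Those SAPs were not among the documents.

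**The concern.** Take a patient suspected of both conditions whose ultrasound confirms DVT and who has no chest imaging. VTE is confirmed, so no follow-up is required, and there is no PE imaging either. Section 6.1 does not remove the patient: it drops those "for whom a final VTE diagnosis according to site's SOC is not available will be excluded from the study", and this patient has a final VTE diagnosis.

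If 9.4 puts this patient in the PE set regardless, only two scores are open: PE-positive on the strength of a DVT, or PE-negative without verification. A similar question arises when a PE-suspect with a negative device result develops a DVT during follow-up. Under the VTE wording of 9.3 that is a false negative in the PE set; under an indication-specific reference it is not.

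Sensitivity is co-primary and rests on few false negatives, so the choice could in principle turn a pass into a fail or a fail into a pass.

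**Working it through.** **Step 1: the text of 9.4.** The first sentence sets the entry condition (valid device result and valid reference value). The second describes who is among those admitted, and the clause on dual-suspects belongs to it. Read in order, a dual-suspect enters each set for which the entry condition is met. The synopsis line concerns enrolment groups, not evaluability.

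**Step 2: which reference is meant.** Section 9.3 says VTE. Section 9.5 uses prevalences of 3.4% (US) and 5.7% (outside the US) for PE against 5.3% and 8.1% for DVT, and reports PE positives as such. Sections 4.2, 9.1, 9.2 and 9.6 all state separate analyses. An indication-specific reference is the reading that fits these. With step 1, the patient confirmed for DVT and never assessed for PE is not evaluable for PE, and the rules do not conflict.

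**Step 3: the plan's own sample size.** The pass rule is an exact two-sided 95% lower limit (LCL) of at least 0.90 and a point estimate of at least 0.95. With 115 positives:
- 5 false negatives: 110/115 = 0.9565, LCL 0.9015, pass.
- 6 false negatives: 109/115 = 0.9478, LCL 0.8899, fail.
- Power at sensitivity 0.98 is P(X ≤ 5) for X ~ Bin(115, 0.02), which is 97.1%. This meets the stated requirement of at least 90%.

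**Step 4: how close to the edge one case can bring the result.**

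| Set | False negatives / positives | LCL | Result |
|---|---|---|---|
| PE, count in 9.5 | 5/121 | 0.9062 | pass |
| PE | 6/121 | 0.8952 | fail |
| PE, one device-negative follow-up DVT added to 5/121 | 6/122 | 0.8960 | fail |
| PE, five device-positive DVT-only subjects added to 6/121 | 6/126 | 0.8992 | fail |
| PE, six such subjects added | 6/127 | 0.90001 | just passes |
| DVT, one device-negative PE event added to 5/115 | 6/116 | 0.8908 | fail |

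At sensitivity 0.98 with 121 positives, exactly 5 false negatives has probability 6.1% and exactly 6 has 2.4%. These are chances of standing next to the boundary. They are not chances that the verdict changes, which also needs affected subjects of the right kind, and their number is not given.

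**Step 5: power if some subjects drop out.** Suppose 0, 6, 10 or 21 of the 121 had no PE-specific reference (assumed numbers). Then 121, 115, 111 or 100 positives remain, and power at 0.98 is 96.5%, 97.1%, 92.7% or 94.9%. It does not fall steadily because the permitted number of false negatives moves in whole steps (5, 5, 4, 4).

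**The case for a change.** The strongest argument for acting is that 9.3 taken literally gives the DVT-confirmed patient a valid, positive VTE reference. The validity condition in 9.4 would then not exclude the patient, and a DVT could count as a PE true positive. The later SAPs can choose a scoring rule, but they cannot supply a reference that was never collected. Reference-positive counts also steer blind sample size re-estimation, so who counts matters while DVT enrolment is open.

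Part of this stands. The wording of 9.3 is loose, and the supplied text does not assign a follow-up event of the other indication.

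The rest is weaker. The any-VTE reading does not fit the way 9.5 counts. The fail-to-pass scenario also mixes the two readings: it treats the 121 as PE-specific and then adds DVT-only cases as PE positives. If scoring were any-VTE, such cases might already be among the 121. Sections 6.2 and 6.7 set a minimum for follow-up and do not show that second-site imaging or follow-up is absent for these patients. The flow diagrams in 4.2 are not visible in the text reviewed.

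For follow-up events of the other indication, both rules are defensible. Counting an event only in its own set matches the separate indications but is the more lenient to the device: it keeps 5/121 (pass) where any-VTE scoring gives 6/122 (fail). Any-VTE scoring matches 9.3 and the aim of safe exclusion, but it charges a PE analysis with a DVT. The documents give no ground for imposing either. Under 9.2, device results stay in a separate file until data lock, after the SAPs are signed, so the sponsor would be choosing without sight of the false negatives.

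**Conclusion.** No change to the plan follows. The apparent contradiction goes away when the inclusion of dual-suspects in 9.4 is read under that section's valid-reference condition and with the separate PE and DVT counts in 9.5. Writing this out would record what the plan already implies, and it would not create the missing second reference.

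The handling of follow-up events of the other indication is unstated in the supplied text. It is a choice between two reasonable rules, and the separate SAPs, due before the first data lock, are the natural place for it. If those SAPs were also silent, this residual point would carry more weight.

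The size cannot be estimated: the numbers of dual-suspects, of those verified for one condition only, and of follow-up events of the other indication are not given. One device-negative event could matter if the result were already at 5 false negatives, which has probability 6.1% for PE at the planned sensitivity. Power stays above 90% at each of the counts checked, and NPV, with near 100% planned power, is little affected. The conclusion rests on the 121 being PE cases, as 9.5 says (uncleaned data), and on the ordinary reading of 9.4.
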